4. PATIENT REGISTRATION/RANDOMIZATION

Note: All patients can be registered following eligibility confirmation by calling the coordinating center study liaison, [name], BSN:

[name]
 [name]
 [name]
 [contact]
 [contact]
 E-mail: [contact]

For questions regarding the eligibility of subjects, please contact the study doctor, [name], at [contact].

Registration will require the following information: 1) your name, telephone and email; 2) protocol name and number; 3) date treatment begins; 4) subject name; 5) date of birth; 6) subject hospital medical record number; 7) primary study physician; 8) primary treatment institution; 9) confirmation of eligibility; 10) copies of the informed consent signature page and 11) verification that the informed consent was signed.

Randomization will occur at the UPCI Biostatistics Core once consent and eligibility are verified.

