1.1.1 Carcinogen-Induced HNSCC

The classic environmental risk factors for HNSCC are tobacco and alcohol exposure. Even when treated with cisplatin-RT, patients with carcinogen-induced PULA HNSCC have poor OS, PFS and LRC. In RTOG 0129⁶ patients with human papillomavirus (HPV)(-) tumors had an absolute 25.1% reduction in OS at 3 years (57.1% vs. 82.4%) vs. patients with HPV(+) tumors, with similar reductions in PFS and LRC. Poor outcomes persist despite intensification with altered fractionation,⁷ multi-drug induction,⁸ or EGFR-targeted monoclonal antibodies (mAb).⁹ For HPV(-) patients, new intensification approaches are a major unmet need.

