3. PATIENT SELECTION

3.1 Inclusion Criteria

Each patient must meet all of the following inclusion criteria to be enrolled in the study:

- Patients must have histologically-confirmed head and neck squamous cell carcinoma with no evidence of distant metastasis. The primary site may be the oral cavity, oropharynx, larynx, or hypopharynx. Patients with squamous cell carcinoma of unknown primary, metastatic to cervical lymph nodes, are permitted to enroll.
- Patients must have high risk or intermediate risk disease, defined below. Staging evaluation should be determined by imaging studies and complete head and neck exam in accordance with the American Joint Committee on Cancer Staging Manual, 7th edition.
 - High risk patient must meet one of the following criteria:
 - Surgically unresectable oral cavity. Patients who are technically resectable but refuse surgery due to morbidity (eg. total glossectomy) are also eligible. Medically inoperable patients are not eligible.
 - Larynx: T4 any N; T2-3 and \geq N2a.

- Hypopharynx: T1-2N1-3 or T3-4N0-3.
- Oropharynx: p16(-) AND T3-4 or \geq N2a.
- Unknown primary: p16(-) AND \geq N2a.

- Intermediate risk patients must meet one of the following criteria:
 - Oropharynx: p16(+) AND one of the following
 - T3 or \geq N2a AND \geq 10 pack-years tobacco exposure (see Tobacco Assessment Form, Appendix A).
 - T4 or N3 disease irrespective of tobacco exposure.
 - Unknown primary: p16(+) AND one of the following
 - \geq N2a AND \geq 10 pack-years tobacco exposure.
 - N3 disease irrespective of tobacco exposure.

Note: for patients with oropharyngeal or unknown primary tumors, p16 status must be known, and can be performed at the local site. p16-positive disease is defined as \geq 70% of tumor cells demonstrating diffuse nuclear and cytoplasmic staining by p16 immunohistochemistry (IHC). A positive test for HPV-16 by in-situ hybridization (ISH), if this is the local site preference for assessing HPV status, may substitute for p16 IHC testing. p16 staining is not required for non-oropharyngeal sites.

- Patients must be untreated with curative-intent surgery for current diagnosis of Stage III, IVa, or IVb disease. Diagnostic biopsy of primary tumor and/or nodal sites is permitted.
 - Diagnostic simple tonsillectomy is permitted, provided patient has RECIST-measurable nodal disease.

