9. STATISTICAL METHODS

This is a randomized, parallel group, non-comparative phase II trial evaluating the safety and efficacy of two schedules of fixed-dose pembrolizumab combined with standard cisplatin-IMRT in intermediate or high risk, PULA HNSCC: sequential and concurrent. This study is being performed in order to provide: a) necessary safety experience; b) preliminary efficacy estimates; c) characterization of the PD-L1 biomarker in the context of definitive chemoradiation; d) the recommended schedule for definitive testing.

Primary Objective

To evaluate two schedules of fixed-dose pembrolizumab (concurrent vs. sequential) added to standard, concurrent cisplatin-IMRT in patients with PULA HNSCC, in order to recommend the schedule to be tested in a subsequent definitive, randomized study.

Sample Size Determination

The target sample size is 40 evaluable patients per arm. Assuming 10% drop out or ineligibility, 90 patients will be randomized (all evaluable patients will be analyzed). The sample size is determined based upon the following assumptions: 1) the 1-year PFS in the high risk population treated with conventional cisplatin-radiotherapy is 60%;⁶ 2) As defined, DLTs occurring in more than 20% of the study population are unacceptable and would constitute an unsafe regimen; 3) The study requires adequate power to detect a signal of antagonism, defined as a 1-year local failure rate

[figure not shown]
exceeding 60%. To advance to Phase II/III testing, a treatment arm must meet all of the following criteria:

- DLT occurs in $\leq 20\%$
- 1-year local failure rate is $< 60\%$
- 1-year PFS is $\geq 60\%$

If both arms meet the above criteria, then the treatment arm demonstrating numerically superior 1-year PFS will advance for definitive testing, as in a so-called “pick-the-winner” trial model. An early phase trial cannot provide the statistical power required for a formal statistical comparison between arms.

The graphic in Figure 1 below demonstrates the probability of accepting either treatment (that is, based on $n = 40$ evaluable patients per arm) by means of 90% one-sided exact confidence intervals (CI) for DLT, 1-year failure rate, and 1-year PFS. If the upper bound of the DLT CI is less than 0.20, the upper bound of the failure CI is less than 0.60, and the lower bound of the 1-year PFS CI is greater than 0.60, the treatment will be accepted.

Figure 1: Probability of accepting the treatment according to the three primary metrics

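### The choice between schedules rests on crude 1-year PFS in a mixed-risk population, with no stratification in the supplied randomisation text and no risk-adjusted comparison; the effect is modest and cheap to remove

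*Combined protocol and SAP*

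**What the plan says.** Section 3.1 admits two defined groups: "Patients must have high risk or intermediate risk disease, defined below". It gives no cap on either group and no expected share. Section 1.1.2 names HPV status and tobacco pack-years as the main determinants of overall survival, with nodal stage next. Section 1.1.1 reports that HPV-negative "tumors had an absolute 25.1% reduction in OS at 3 years" (57.1% v 82.4%), with similar reductions in PFS and locoregional control.

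On allocation, section 4 states: "Randomization will occur at the UPCI Biostatistics Core once consent and eligibility are verified". No stratification, blocking or minimisation is named there or elsewhere in the supplied text.

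Section 9 (Sample Size Determination) sets the selection rule: "If both arms meet the above criteria, then the treatment arm demonstrating numerically superior 1-year PFS will advance for definitive testing". It states no minimum margin and no adjustment. The Analysis Plan in the same section calculates proportions with exact 90% intervals. Its only covariate analysis is logistic regression on baseline PD-L1, which is not linked to the selection.

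**The concern.** The primary objective is to recommend one schedule. When both arms meet the three criteria, that recommendation is a direct comparison of two point estimates from 40 patients each. If the arms differ by chance in the share of better-prognosis patients, the difference passes straight into the estimates, and with no margin one patient can decide. The schedule taken into a definitive trial could then partly reflect who was allocated to it. If the winning arm turned out to hold more intermediate-risk patients, the plan would offer no prespecified way to show that the choice survives adjustment.

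**Working it through.** **The plan's own figure.** "The target sample size is 40 evaluable patients per arm"; "Assuming 10% drop out or ineligibility, 90 patients will be randomized". 40/0.9 = 44.4, rounded up to 45 per arm, and 2 x 45 = 90, so the stated number reproduces. The 40 rests on Figure 1, which is not shown, so no power figure can be checked.

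**Inputs from the documents.** 40 evaluable patients per arm. For the baseline, section 9 assumes "the 1-year PFS in the high risk population treated with conventional cisplatin-radiotherapy is 60" percent.

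**Assumptions (not in the documents).** Simple randomisation; intermediate-risk share q of 30% or 50%; 1-year PFS higher in intermediate- than in high-risk patients by a gap of 10 to 25 points; 1-year status known for all evaluable patients; ties split evenly.

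**Step 1: size of the imbalance.** The SD of the between-arm difference in intermediate-risk share is sqrt(2q(1-q)/40). This is sqrt(2 x 0.3 x 0.7/40) = 0.102 at q = 30% and sqrt(2 x 0.5 x 0.5/40) = 0.112 at q = 50%. A difference of 15 points is 6 patients of 40. Exact binomial probabilities of 6 or more in either direction are 17.9% and 21.9%.

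**Step 2: effect on PFS.** A 15-point imbalance shifts the crude PFS difference by 0.15 x gap. That is 1.5 points (0.6 patients of 40) at a 10-point gap and 3.75 points (1.5 patients) at 25. Arms tie or differ by one patient in about 18% of trials at a true 75% v 65%, and in up to about 29% when the schedules are equal.

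**Step 3: share of the noise due to risk mix.** The variance from mix is gap^2 x 2q(1-q)/40, and the total with equal arms is 2p(1-p)/40.
- q = 50%, gap 25, high-risk PFS 60%, so p = 72.5%: 0.0625 x 0.0125 = 0.00078 against 2 x 0.725 x 0.275/40 = 0.00997, or 8%.
- q = 30%, gap 10, so p = 63%: 0.01 x 0.0105 = 0.000105 against 2 x 0.63 x 0.37/40 = 0.01166, or 1%.

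**Step 4: effect on the choice.** I simulated 600,000 trials per scenario. The standardised estimate is the within-group PFS averaged over the pooled risk mix. Equal schedules have high-risk PFS at 60%; otherwise overall PFS is 75% v 65%.

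| | Gap 10 points | Gap 25 points |
|---|---|---|
| Equal schedules: crude and standardised winners opposite | about 1% | 4-5% |
| 75% v 65%: correct pick, crude | 83.5-83.6% | 83.5% |
| 75% v 65%: correct pick, standardised | 83.6-83.7% | 84.3-84.4% |
| Better arm's mix worse by 15 points or more: crude v standardised | 78-79% v 83-84% | 70-71% v 84% |
| Better arm's mix better by 15 points or more: crude v standardised | 88% v 83% | 93% v 84% |

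The last two rows occur equally often, in about 9-11% of trials each.

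**Step 5: the advancement criteria.** The rows above do not apply them. Under the confidence-bound wording, PFS must reach 29/40 (one-sided 90% exact lower limit 0.615; 28/40 gives 0.588). At 75% v 65% both arms reach this in about 15% of trials. Among those, the gain from standardising is up to about 2 points. Under the point-estimate wording (24/40 or more) both arms pass in about 79%. The DLT and local-failure criteria were not simulated.

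**The case against.** Several objections have force.

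- **The average gain is under one point.** This stands. The plan's dominant weakness for selection is sampling noise at 40 per arm, and neither stratification nor standardisation changes that.
- **The unfavourable-draw contrast (about 70% v 84%) is only half the picture.** This also stands. A reader might take it as the benefit of adjusting, but in the equally frequent mirror case crude selection does better (93% v 84%). The two nearly cancel, leaving the small net gain.
- **The 25-point gap does not belong to these risk groups.** It is 3-year overall survival by HPV status. Section 3.1 admits p16-positive patients only with tobacco exposure plus stage, or with T4 or N3 disease, so many of the best-prognosis HPV-positive patients are excluded. Under a constant hazard (an assumption), 57.1% and 82.4% at 3 years become 0.571^(1/3) = 83.0% and 0.824^(1/3) = 93.8% at 1 year, an 11-point gap in survival. Hence the 10- to 25-point range.
- **Stratification may exist.** A reader might infer that the trial was not stratified. The documents do not support that: some front matter was not supplied, and allocation is run centrally. What can be said is that the supplied randomisation text names no factor.
- **The trial is declared non-comparative.** This does not answer the point. Disclaiming a formal test does not alter the fact that the rule ranks the arms on PFS.

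**Conclusion.** The point holds at minor priority. The selection rule uses crude PFS in a mixed-risk population and nothing in the visible plan adjusts for risk. Under the stated assumptions, risk mix reverses about 1-5% of choices when the schedules are equal. Standardising improves correct selection at a true 10-point difference by about 0.1-0.9 points on average, or up to about 2 points among trials where both arms pass the confidence-bound PFS criterion. It did not lower average correct selection at that difference in any scenario run.

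A reader might infer that risk imbalance is the main route to a wrong schedule. The figures do not support that: it accounts for about 1-8% of the variance of the PFS difference in the two cases worked above, and the rest is mainly sampling noise. The sizes depend on an intermediate-risk share and a 1-year PFS gap that the documents do not give. The value of the change lies in protection when the arms happen to be imbalanced, and in having the adjusted comparison specified in advance.

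**What to change.** 1. State the randomisation method in section 4 and, if not already done, stratify by risk group (high v intermediate) as defined in section 3.1.
2. In section 9, prespecify that when both arms meet the three criteria, the choice uses 1-year PFS standardised to the pooled risk mix: within each arm, average the high- and intermediate-risk proportions with weights equal to each group's share of all evaluable patients. Report crude PFS alongside. The three criteria and their exact intervals can stay as they are.
3. Record risk group as a data item. It can be derived from the eligibility data, but the registration list in section 4 asks only for confirmation of eligibility.

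The cost is one factor in the allocation list, one derived variable and one line of analysis, with no extra patients, visits or procedures. If accrual has begun, the analysis change alone is enough, provided it is fixed before 1-year PFS is compared by arm.

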5. TREATMENT PLAN

Arm 1 (Table 2): Pembrolizumab will be initiated 2 weeks after the completion of cisplatin-IMRT (week 9 of protocol treatment) and administered at the fixed dose of 200 mg IV q 3 weeks (+/- 3 days) for a total of 24 weeks (8 doses; 6 months). NOTE: Per discretion of the treating investigator, the week 9 dose of pembrolizumab may be delayed up to 3 weeks for recovery of acute toxicities from chemoradiotherapy. This dose would be considered delayed, and all subsequent doses would be administered at a q 3 week interval (+/- 3 days) from first pembrolizumab dose.

Arm 2 (Table 3): Pembrolizumab will be initiated 1 week prior to cisplatin-IMRT (the “window”) at the dose of 200 mg IV q 3 weeks (+/- 3 days). Pembrolizumab will be continued concurrently through cisplatin-IMRT (weeks 3, 6), and continued for a 15 week maintenance period after completion of cisplatin-IMRT for a total pembrolizumab treatment period of 24 weeks (8 doses; 6 months). NOTE: Per discretion of the treating investigator, the week 9 dose of pembrolizumab may be delayed up to 3 weeks for recovery of acute toxicities from chemoradiotherapy. This dose would be considered delayed, and all subsequent doses would be administered at a q 3 week interval (+/- 3 days) until completion.

Table 2. Arm 1 Treatment Plan

ARM 1	Week of Treatment														
	1	2	3	4	5	6	7	9	12	15	18	21	24	25	30
IMRT	X	X	X	X	X	X	X								
Cisplatin	X	X	X	X	X	X	X								
Pembrolizumab								X	X	X	X	X	X	X	X

Table 3. Arm 2 Treatment Plan

ARM 2	Week of Treatment													
	-1	1	2	3	4	5	6	7	9	12	15	18	21	
IMRT		X	X	X	X	X	X	X						
Cisplatin		X	X	X	X	X	X	X						
Pembrolizumab	X			X			X		X	X	X	X	X	

5.1 Study Drug Administration: Pembrolizumab

5.1.1 Route of Administration

Pembrolizumab will be administered as an IV infusion.

5.1.2 Doses to be Administered

The dose of pembrolizumab will be 200 mg (fixed dose) IV every 3 weeks (+/- 3 days), beginning on week 9 of treatment (Arm 1) or beginning one week (week -1) prior to concurrent cisplatin-IMRT (in Arm 2).

5.1.3 Dosing Schedule

Subjects will receive pembrolizumab once every 3 weeks (+/- 3 days) in an IV infusion over 30 minutes.

Sites should make every effort to target infusion timing to be as close to 30 minutes as possible. However, given the variability of infusion pumps from site to site, a window of -5 minutes and +10 minutes is permitted (i.e., infusion time is 30 minutes: -5 min/+10 min).

The Pharmacy Manual contains specific instructions for the preparation of the pembrolizumab infusion fluid and administration of infusion solution.

5.1.4 Order of Administration

When cisplatin and pembrolizumab are administered on the same day in Arm 2, pembrolizumab should follow cisplatin. Pembrolizumab may be given either before or after the radiation therapy fraction that is given the same day.

5.1.5 Prohibited Concomitant Medications

Subjects are **prohibited** from receiving the following therapies during the Screening and Treatment phases of this trial:

- Colony stimulating factors, including G-CSF, pegylated G-CSF, and erythropoietin analogs.
- Immunotherapy not specified in this protocol.
- Chemotherapy not specified in this protocol.
- Radiation not specified in this protocol.
- Investigational agents other than pembrolizumab.
- Live vaccines within 30 days prior to the first dose of trial treatment and while participating in the trial. Examples of live vaccines include, but are not limited to, the following: measles, mumps, rubella, chicken pox, yellow fever, rabies, BCG, and typhoid (oral) vaccine. Seasonal influenza vaccines for injection are generally killed virus vaccines and are allowed; however intranasal influenza vaccines (e.g. Flu-Mist®) are live attenuated vaccines, and are not allowed.
- Glucocorticoids for any purpose other than the following two clinical situations:
 - To control cisplatin-related nausea, if viewed as absolutely necessary for symptom control by the treating medical oncologist. NOTE: every effort will be made to minimize glucocorticoid administration either as premedication or as prophylaxis/treatment of delayed nausea from cisplatin.
 - To modulate symptoms from an event of clinical interest of suspected immunologic etiology.

Subjects who, in the assessment of the treating investigator, require the use of any of the aforementioned treatments for clinical management should be removed from the trial. Subjects may receive other medications that the investigator deems to be medically necessary.

There are no prohibited therapies during the Post-Treatment or Follow-up phases of this trial.

5.2 Drug Administration – Cisplatin

5.2.1 Route of Administration

Cisplatin will be administered as an IV infusion.

5.2.2 Doses to be Administered

The starting dose of cisplatin will be 40 mg/m² weekly (+/- 3 days), beginning concurrent with IMRT during week 1 of study treatment in both Arms (see Tables 2 and 3). The actual body weight will be used for all patients. There should be no dose modifications because of obesity.

5.2.3 Dosing Schedule

Patients will receive cisplatin once weekly as an IV infusion over 60 minutes, for a total of 7 doses.

Cisplatin should be administered on Monday, Tuesday, or Wednesday of each treatment week and may be given either before or after the radiation therapy fraction that is given on the same day. When cisplatin and pembrolizumab are administered on the same day, pembrolizumab should follow cisplatin.

5.2.4 Concomitant Medications during Cisplatin Infusion

5.2.4.1 Nausea

Cisplatin, 30-40 mg/m², is a moderately emetogenic drug. For acute nausea and vomiting, premedication should include a 5-HT3 antagonist, such as granisetron 1 mg iv; ondansetron, up to 16 mg iv; or palonosetron, 0.25 mg iv. Palonosetron has a longer half-life (40h) than the first generation 5HT3 antagonists. NOTE: The use of a corticosteroid premedication, such as dexamethasone 10 mg IV, is typically combined with a 5-HT3 antagonist when administering weekly cisplatin. In this protocol, omitting scheduled corticosteroid premedication, due to the immunosuppressive properties, is strongly encouraged on both study arms. However, if necessary in the judgment of the treating investigator, a corticosteroid may be administered as a premedication for acute nausea/vomiting. Fosaprepitant may be administered in accordance with institutional guidelines or investigator judgment.

Breakthrough nausea and vomiting may be managed at the discretion of the treating investigator. Delayed nausea and vomiting (greater than 24 hours after chemotherapy administration) may be managed per investigator discretion, including use of the following potential nausea regimens: oral metoclopramide 10 mg qid x 2-4 days; prochlorperazine 10 mg qid x 2-4 days; a 5HT3 antagonist (e.g. granisetron, ondansetron) may also be given for up to 3 days (only if palonosetron was not given prior to chemotherapy). Aprepitant may also be used for delayed nausea. NOTE: Although dexamethasone and other corticosteroids are discouraged for delayed cisplatin-induced nausea in this protocol, corticosteroids may be used if viewed as necessary by the treating investigator (e.g. 8 mg bid for 2 days, followed by 4 mg bid for 2 days).

5.2.4.2 Hydration and Electrolyte Support

Patients must receive vigorous hydration and diuresis. Recommendations are to administer cisplatin, 40 mg/m², in NS 1000 ml. Additional IV fluid, potassium chloride, and/or magnesium sulfate may be administered at the discretion of the medical oncologist. Mannitol may be administered at the discretion of the medical oncologist.

5.3 Dose Modifications

5.3.1 Pembrolizumab Dose Modifications

Retreatment criteria for pembrolizumab and cisplatin are independent (retreatment criteria for cisplatin are specified in section 5.3.2 below). There are no dose reductions for pembrolizumab. If the subject meets retreatment criteria, the full dose of 200 mg will be administered. If subjects do not meet retreatment criteria, then the dose of pembrolizumab will be SKIPPED. The sole exception to this rule is the first dose of pembrolizumab following completion of chemoradiotherapy, on both Arms 1 and 2. Although scheduled for

Week 10 of protocol treatment, the first post-chemoradiotherapy dose of pembrolizumab may be DELAYED up to 3 weeks to allow for recovery from acute toxicities, in accordance with the treating investigator's judgment. In the case of such delay, the following three doses of pembrolizumab will then be scheduled every 3 weeks (+/- 3 days) from the first post-chemoradiotherapy dose.

Subjects should receive appropriate supportive care measures as deemed necessary by the treating investigator. Suggested supportive care measures for the management of adverse events with potential immunologic etiology are outlined in Table 4 below and in greater detail below. Where appropriate, these guidelines include the use of oral or intravenous treatment with corticosteroids as well as additional anti-inflammatory agents if symptoms do not improve with administration of corticosteroids. Note that several courses of steroid tapering may be necessary as symptoms may worsen when the steroid dose is decreased. For each disorder, attempts should be made to rule out other causes such as metastatic disease or bacterial or viral infection, which might require additional supportive care. The treatment guidelines are intended to be applied when the investigator determines the events to be related to pembrolizumab.

Note: if after the evaluation the event is determined not to be related to pembrolizumab, the investigator is instructed to follow the Events of Clinical Interest (ECI) reporting guidance but does not need to follow the treatment guidance (as outlined in the ECI guidance document). Please see section 12.4.2 for ECI reporting guidance.

It may be necessary to perform conditional procedures such as bronchoscopy, endoscopy, or skin photography as part of evaluation of the event. Suggested conditional procedures, as appropriate, can be found in the ECI guidance document.

Table 4. Pembrolizumab Dose Modification Guidelines for Drug-Related Adverse Events

Toxicity	Hold Pembrolizumab For NCI CTCAE Grade	Timing for Restarting Treatment	Discontinue Pembrolizumab Permanently
Out-of-field Rash (skin rash outside of the radiation field)	3	Toxicity resolves to Grade 0-1 and the patient has tapered off of or did not require systemic corticosteroids. (Ongoing management with topical steroids is acceptable.)	Toxicity does not resolve within 12 weeks of last dose or inability to taper off of corticosteroids within 12 weeks.
In-field radiation dermatitis (skin rash within the radiation field) – Arm 2	4 ^a	Toxicity resolves to Grade 3 or less. NOTE: systemic and topical steroids should be avoided in the case of radiation dermatitis that is restricted to in-field.	Toxicity does not resolve to Grade 3 or better within 6 weeks of completing IMRT
Diarrhea/Colitis	2-3	Toxicity resolves to Grade 0-1 and the patient has successfully tapered off of corticosteroids.	Toxicity does not resolve within 12 weeks of last dose or inability to taper off of corticosteroids within 12 weeks.
	4	Permanently discontinue	Permanently discontinue
AST, ALT, or Increased Bilirubin	2	Toxicity resolves to Grade 0-1 and the patient has tapered off of corticosteroids.	Toxicity does not resolve within 12 weeks of last dose.
	3-4	Permanently discontinue	Permanently discontinue

Toxicity	Hold Pembrolizumab For NCI CTCAE Grade	Timing for Restarting Treatment	Discontinue Pembrolizumab Permanently
Type 1 diabetes mellitus (if new onset) or Hyperglycemia	T1DM or 3-4	Hold pembrolizumab for new onset Type 1 diabetes mellitus or Grade 3-4 hyperglycemia associated with evidence of beta cell failure.	Resume pembrolizumab when patients are clinically and metabolically stable.
Hypophysitis	2-3	Toxicity resolves to Grade 0-1	Toxicity does not resolve within 12 weeks of last dose or inability to taper corticosteroids to a dose of prednisone 10 mg or less within 12 weeks.
	4	Permanently discontinue	Permanently discontinue
Hyperthyroidism	3	Toxicity resolves to Grade 0-1	Toxicity does not resolve within 12 weeks of last dose or inability to taper off corticosteroids within 12 weeks.
	4	Permanently discontinue	Permanently discontinue
Hypothyroidism	2-4	Therapy with pembrolizumab can be continued while treatment for the thyroid disorder is instituted	Therapy with pembrolizumab can be continued while treatment for the thyroid disorder is instituted.
Infusion Reaction	3-4	Permanently discontinue	Permanently discontinue
Pneumonitis	2	Toxicity resolves to Grade 0-1	Toxicity does not resolve within 12 weeks of last dose or inability taper off corticosteroid within 12 weeks.
	3-4	Permanently discontinue	Permanently discontinue
Renal Failure or Nephritis ^b – Serum/Whole Creatinine	2 ^c	Toxicity resolves to Grade 0-1	Toxicity does not resolve within 12 weeks of last dose or inability to taper off corticosteroid within 12 weeks.
	3-4	Permanently discontinue	Permanently discontinue
All Other Drug-Related Toxicity ^d	3 or Severe	Toxicity resolves to Grade 0-1	Toxicity does not resolve within 12 weeks of last dose or inability taper off of corticosteroids within 12 weeks.
	4	Permanently discontinue	Permanently discontinue

Note: Permanently discontinue pembrolizumab for any severe or Grade 3 drug-related AE that recurs or any life-threatening event.

^a Per investigator discretion, pembrolizumab may be held for grade 3 in-field radiation dermatitis. If pembrolizumab is held for grade 3 in-field radiation dermatitis, no specific grade of resolution is required to restart pembrolizumab; restart would also be per investigator discretion.

^b NOTE: Dose modification of cisplatin in the setting of renal insufficiency is addressed separately in Section 5.3.2.

^c NOTE: if event is considered **clinically unrelated or unlikely to be related to pembrolizumab**, and an alternate clinical explanation is likely, probable, or definite in the judgment of the investigator (example, attributable to cisplatin and/or prerenal azotemia in the setting of nausea, and responding to hydration), then corticosteroids may be omitted and pembrolizumab may be administered.

^d Patients with intolerable or persistent Grade 2 drug-related AE may hold pembrolizumab at physician discretion. Permanently discontinue pembrolizumab for persistent Grade 2 adverse reactions for which treatment with study drug has been held, and that do not recover to Grade 0-1 within 12 weeks of the last dose of pembrolizumab. Note: Pembrolizumab does **not** need to be held for grade 3 dysphagia, grade 3 pain, grade 3 weight loss, or grade 3 fatigue, which are expected toxicities for chemoradiation of HNSCC and will be managed aggressively by treating investigators per standards of care.

- **Pneumonitis:**
 - For **Grade 2 events**, treat with systemic corticosteroids. When symptoms improve to Grade 1 or less, steroid taper should be started and continued over no less than 4 weeks.
 - For **Grade 3-4 events**, immediately treat with intravenous steroids. Administer additional anti-inflammatory measures, as needed.
 - Add prophylactic antibiotics for opportunistic infections in the case of prolonged steroid administration.

- **Diarrhea/Colitis:**

Subjects should be carefully monitored for signs and symptoms of enterocolitis (such as diarrhea, abdominal pain, blood or mucus in stool, with or without fever) and of bowel perforation (such as peritoneal signs and ileus).

- All subjects who experience diarrhea/colitis should be advised to drink liberal quantities of clear fluids (or to administer liberal quantities of clear fluids via PEG tube if present). If sufficient oral or PEG-tube fluid intake is not feasible, fluid and electrolytes should be substituted via IV infusion. For Grade 2 or higher diarrhea, consider GI consultation and endoscopy to confirm or rule out colitis.
- For **Grade 2 diarrhea/colitis** that persists greater than 3 days, administer oral corticosteroids.
- For **Grade 3 or 4 diarrhea/colitis** that persists > 1 week, treat with intravenous steroids followed by high dose oral steroids.
- When symptoms improve to Grade 1 or less, steroid taper should be started and continued over no less than 4 weeks.

- **Type 1 diabetes mellitus (if new onset, including diabetic ketoacidosis [DKA]) or ≥ Grade 3 Hyperglycemia, if associated with ketosis (ketonuria) or metabolic acidosis (DKA):**

- For **T1DM or Grade 3 – 4 Hyperglycemia:**
 - Insulin replacement therapy is recommended for Type I diabetes mellitus and for Grade 3-4 hyperglycemia associated with metabolic acidosis or ketonuria.
 - Evaluate patients with serum glucose and a metabolic panel, urine ketones, glycosylated hemoglobin, and C-peptide.

- **Hypophysitis:**

- For **Grade 2** events, treat with corticosteroids. When symptoms improve to Grade 1 or less, steroid taper should be started and continued over no less than 4 weeks. Replacement of appropriate hormones may be required as the steroid dose is tapered.
- For **Grade 3-4** events, treat with an initial dose of IV corticosteroids followed by oral corticosteroids. When symptoms improve to Grade 1 or less, steroid taper should be started and continued over no less than 4 weeks. NOTE: Replacement of appropriate hormones may be required as the steroid dose is tapered.

- **Hyperthyroidism or Hypothyroidism:**

Thyroid disorders can occur at any time during treatment with pembrolizumab. Of note, patients with HNSCC undergoing cisplatin-IMRT may experience subclinical mild hyperthyroidism or euthyroid sick syndrome during IMRT, and commonly develop late hypothyroidism as a consequence of radiation dose to the thyroid. Monitor patients for changes in thyroid function (TSH and free T4 every 3 weeks on Arms 1 and 2, and as indicated based on clinical evaluation) and for clinical signs and symptoms of thyroid disorders. No intervention is required for Grade 1 hyperthyroidism or hypothyroidism events.

- **Grade 2** hyperthyroidism events:
 - In hyperthyroidism, non-selective beta-blockers (e.g. propranolol) are suggested as initial therapy.
- **Grade 3-4** hyperthyroidism events:
 - Treat with an initial dose of IV corticosteroid followed by oral corticosteroids. When symptoms improve to Grade 1 or less, steroid taper should be started and continued over no less than 4 weeks. Replacement of appropriate hormones may be required as the steroid dose is tapered.

- **Grade 2-4 hypothyroidism**
 - Hypothyroidism is a common consequence of chemoradiotherapy for HNSCC, and is likely permanent. In Grade 2-4 hypothyroidism, thyroid hormone replacement therapy, with levothyroxine or liothyroinine, is indicated per standard of care.
- **Hepatic:**
 - For **Grade 2** events, monitor liver function tests weekly until returned to baseline values
 - Treat with IV or oral corticosteroids.
 - For **Grade 3-4** events, hospitalization is indicated. Treat with intravenous corticosteroids for 24 to 48 hours. Monitor liver function tests frequently.
 - When symptoms improve to Grade 1 or less, a steroid taper should be started and continued over no less than 4 weeks.
- **Renal Failure or Nephritis:**

Mild to moderate renal insufficiency can occur in the context of cisplatin chemotherapy. Dose modification of cisplatin in the setting of renal insufficiency is addressed separately in Section 5.3.2.

 - For **Grade 2** events at least possibly related to pembrolizumab, hold pembrolizumab and treat with vigorous hydration and oral corticosteroids. Monitor renal function weekly until returned to baseline values. NOTE: if event is considered ***clinically unrelated or unlikely to be related to pembrolizumab***, and an alternate clinical explanation is likely, probable, or definite in the judgment of the investigator (example, attributable to cisplatin and/or prerenal azotemia in the setting of nausea, and responding to hydration), then corticosteroids may be omitted and pembrolizumab may be administered.
 - For **Grade 3-4** events, hospitalization is indicated. Treat with vigorous hydration and IV corticosteroids for 24 to 48 hours. Monitor renal function frequently. Consultation with nephrology is recommended.
 - When symptoms improve to Grade 1 or less, steroid taper should be started and continued over no less than 4 weeks.

Management of Infusion Reactions: Signs and symptoms usually develop during or shortly after drug infusion and generally resolve completely within 24 hours of completion of infusion. Table 5 below shows treatment guidelines for subjects who experience an infusion reaction associated with administration of pembrolizumab.

Table 5. Infusion Reaction Treatment Guidelines

NCI CTCAE Grade	Treatment	Premedication at subsequent dosing
Grade 1 Mild reaction; infusion interruption not indicated; intervention not indicated	Increase monitoring of vital signs as medically indicated until the subject is deemed medically stable in the opinion of the investigator.	None
Grade 2 Requires infusion interruption but responds promptly to symptomatic treatment (e.g., antihistamines, NSAIDS, narcotics, IV fluids); prophylactic medications indicated for <=24 hrs	Stop Infusion and monitor symptoms. Additional appropriate medical therapy may include but is not limited to: IV fluids Antihistamines NSAIDS Acetaminophen Narcotics Increase monitoring of vital signs as medically indicated until the subject is	Subject may be premedicated 1.5h (\pm 30 minutes) prior to infusion of pembrolizumab with: Diphenhydramine 50 mg po (or equivalent dose of antihistamine).

NCI CTCAE Grade	Treatment	Premedication at subsequent dosing
	
deemed medically stable in the opinion of the investigator.
 
If symptoms resolve within one hour of stopping drug infusion, the infusion may be restarted at 50% of the original infusion rate (e.g., from 100 mL/hr to 50 mL/hr). Otherwise dosing will be held until symptoms resolve and the subject should be premedicated for the next scheduled dose.
 
Subjects who develop Grade 2 toxicity despite adequate premedication should be permanently discontinued from further pembrolizumab administration.
	Acetaminophen 500-1000 mg po (or equivalent dose of antipyretic).
Grades 3 or 4 Grade 3: Prolonged (i.e., not rapidly responsive to symptomatic medication and/or brief interruption of infusion); recurrence of symptoms following initial improvement; hospitalization indicated for other clinical sequelae (e.g., renal impairment, pulmonary infiltrates) Grade 4: Life-threatening; pressor or ventilatory support indicated	
Stop Infusion.
 
Additional appropriate medical therapy may include but is not limited to:
 
 IV fluids Antihistamines NSAIDS Acetaminophen Narcotics Oxygen Pressors Corticosteroids Epinephrine 
Increase monitoring of vital signs as medically indicated until the subject is deemed medically stable in the opinion of the investigator.
 
Hospitalization may be indicated.
 
Subject is permanently discontinued from further pembrolizumab administration.
	No subsequent dosing of pembrolizumab
Appropriate resuscitation equipment should be available in the room and a physician readily available during the period of drug administration.		

